I agree to have control over all clinical supplies and the investigational product provided by CathVision. I further agree not to originate or use the name of CathVision ApS and/or ECGenius® System, or any of its employees, in any publicity, news release or other public announcements, written or oral, whether to the public, press or otherwise, relating to this protocol, to any amendment hereto, or the performance hereunder, without the prior written consent of CathVision ApS.

[figure not shown]

I herewith declare that I agree with the protocol described in detail in this document and agree to conduct the study in accordance with the protocol and compliance with Good Clinical Practice and all applicable regulatory requirements.

INVESTIGATOR SIGNATURE

Signature	Location	Date
Name: <Enter>		dd-Mmm-yyyy
<Title>		

PROTOCOL SYNOPSIS

Title	A Prospective, Multi-Center, Open-Label, Single-Arm Study to Evaluate the Safety and Technical Performance of the CathVision ECGenius® System
Investigational device	
The CathVision ECGenius® System is an electrophysiology (EP) recording system to be used in EP studies as a tool to monitor, display, and record signals of the heart and cardiac arrhythmias.
 
Intended Use	To acquire, amplify, digitize, stream atrial and ventricular intracardiac electrophysiology signals during cardiac electrophysiology studies and related procedures.
Objective	The primary objective is to evaluate the safety and technical performance of the CathVision ECGenius® System. The secondary objective is to benchmark the intracardiac electrogram signal quality compared to commercially available systems in patients undergoing assessment and ablation of cardiac arrhythmias.
Study Design	
A prospective, multi-center, open-label, single-arm study to evaluate the safety and technical performance of the CathVision ECGenius® system.
 
Patients who are scheduled to undergo an EP procedure and meet the inclusion/exclusion criteria will be enrolled in the study. Intracardiac signals will be passively recorded using CathVision ECGenius® System in parallel with the commercial EP recording system.

Sample size	Up to 30 subjects shall be enrolled in the study.
Investigational Sites	Up to two (2) investigational sites in the United States.
Study Duration / Follow-up Period	Study enrollment is planned for 1-3 months.

Primary Endpoint	
The Primary endpoint of the study will be evaluated as the safety and technical success of CathVision ECGenius® System to collect and record intracardiac signals during EP procedures. With focus on:
 
 • To record and plot low voltage electrograms • To assess the improved signal (better signal to noise ratio) compared with the standard signal • To visualize the shape and timing of electrograms
Secondary Endpoint	
The Secondary endpoint of the study will be evaluated as the technical performance of CathVision ECGenius® System during routine EP procedures.
 
 • To log time stamp for arrhythmia termination when termination is successful • To confirm compatibility of CathVision ECGenius® system with commercially available 3D mapping systems and with available intracardiac catheters. • To have no or minimal device malfunctions reported with the use of the CathVision ECGenius®
Entry Criteria	
Inclusion Criteria Eligible subjects will meet ALL the following inclusion criteria:
 
 1. Patient is scheduled for catheter ablation or diagnostic electrophysiology procedure. 2. At least 18 years of age. 3. Able and willing to provide informed consent or obtain consent from a legally authorized representative (LAR). 
Exclusion Criteria Eligible subjects will not meet ANY of the following exclusion criteria:
 
 1. Patient inability to understand or refusal to sign informed consent. 2. Patient is a prisoner or under incarceration 3. Patients who in the opinion of the physician are not candidates for this study.

TABLE OF CONTENTS

1.	INTRODUCTION	11
1.1	Cardiac Electrophysiology	11
1.2	Intracardiac Electrophysiology Signals During Cardiac Electrophysiology Studies	11
1.3	Rationale for this Clinical Investigation	11
2.	DEVICE DESCRIPTION	12
2.1	Signal Processing Overview	12
3.	RISK-BENEFIT ANALYSIS	13
4.	INVESTIGATIONAL PLAN	14
4.1	Study Objectives	14
4.2	Study Design	14
4.3	Study Duration	14
4.4	Subject Population	14
4.4.1	Inclusion Criteria	14
4.4.2	Exclusion Criteria	15
4.5	Study Outcomes	15
4.5.1	Primary Outcome	15
4.5.2	Secondary Outcome	15
4.6	Study Procedures	15
4.6.1	Informed Consent	15
4.6.2	Subject Identification	16
4.7	Study Visits	17
4.7.1	Schedule of Assessments	17
4.7.2	Visit 1: Day -15 ± 15 (screening visit)	17
4.7.3	Screen Failures	17

1. INTRODUCTION

1.1 CARDIAC ELECTROPHYSIOLOGY

Of the total worldwide population, 1% and 2% of rural and urban areas suffer from cardiac arrhythmia, respectively. Approximately 15% of patients do not respond to drug treatment and need a device-based interventional treatment. As a result, there is a great need for cardiac arrhythmia ablation. Today, however, the exact identification of the mechanism of the arrhythmia and subsequent successful ablation treatment are challenging for physicians. The three most prevalent arrhythmias (“complex arrhythmias”) for catheter ablation are atrial fibrillation, atrial tachycardia, and ventricular tachycardia.

1.2 INTRACARDIAC ELECTROPHYSIOLOGY SIGNALS DURING CARDIAC ELECTROPHYSIOLOGY STUDIES

Cardiac electrograms are generated by the potential (voltage) differences recorded at two recording electrodes during the cardiac cycle. All clinical electrogram recordings are differential recordings from one source that is connected to the anodal (positive) input of the recording amplifier and a second source that is connected to the cathodal (negative) input. Unipolar recordings are obtained by positioning the exploring electrode in the heart and the second electrode (referred to as an indifferent electrode) distant (theoretically an infinite distance) from the heart such that it has little or no cardiac signal.

Bipolar recordings are obtained by connecting two electrodes that are exploring the area of interest to the recording amplifier. At each point in time, the potential generated is the sum of the potential from the positive input and the potential at the negative input. The potential at the negative input is inverted and thus subtracted from that at the positive input. Because the far-field signal is similar at each instant in time, it is largely subtracted out, leaving the local signal. In a homogeneous sheet of tissue, the initial peak of the bipolar signal coincides with depolarization beneath the recording electrode. [2]

1.3 RATIONALE FOR THIS CLINICAL INVESTIGATION

Electrograms and their interpretation are a key tool for electrophysiologists to target ablation sites and are acquired from electrodes on intracardiac diagnostic catheters and surface Electrocardiograms (ECGs). Besides the dominant noise contributor of 50/60Hz from the main power line, there are noise contributors from stimulation, ablation, and defibrillation artifacts that disturb the clear view of electrophysiological signals. Stimulation artifacts today are a result of (poor) software filter design, whereas ablation artifacts are mostly a hardware problem from the high energy exposure on the ablation tip electrode that is also used for measurements.

Baseline noise peak-to-peak levels below 15 μ V in bipolar recordings and below 30 μ V in unipolar recordings would be considered best-in-class. Bipolar recordings between adjacent band electrodes are the most commonly used and practically they are often “derived bipolar”. This means they are individual signals first amplified against a different but common reference, and then subtracted from each other. Unipolar recordings are important for advanced algorithms, such as 3D mapping

and rotor mapping for atrial fibrillation. The unipolar reference is most often Wilson Central Terminal (WCT), but it can also be a distant intracardiac electrode.

Electrograms are usually sampled at 1 to 2kHz, and bandpass filtered at 30 to 500Hz for bipolar and 0.5 to 300Hz for unipolar recordings. 64 to 160 channels are the typical capacity of recording systems today.

In the operating room, other devices and technologies are present: 3D mapping (triangulation of catheter tip position with impedance- and magnetic technology, <0.2 gauss), fluoroscopy/X-ray, Radiofrequency (RF) generator, cryo gas station, stimulator, saline coolant pump for ablation catheter RF-tip irrigation, hemodynamics, magnetic catheter steering (0.08T).

It is not unusual to defibrillate the patient to cardiovert them from an arrhythmia. It is not unusual that patients have implanted cardioverter-defibrillators (ICDs).

It is CathVision's goal to develop a new electrophysiology recording system with improved signal quality particularly of unipolar recordings, with fast pacing and defibrillation recovery times, and with minimal or reduced RF ablation artifacts. The reduction in noise and artifacts will allow for better diagnosis and delivery of advanced ablation therapy in arrhythmia patients.

[figure not shown]
2. DEVICE DESCRIPTION

The CathVision ECGenius System is an electrophysiology (EP) recording system to be used in EP studies as a tool to monitor, display, and record signals of the heart and cardiac arrhythmias. The investigational device ECGenius System includes the following items:

- EP amplifier (EPAMP)
- Pin box cable assembly for connection of catheters
- Surface ECG cable
- Data cable to host computer
- Recording system software (RECORDER SW)
- Host computer (ECGenius PC) and monitors

2.1 SIGNAL PROCESSING OVERVIEW

The main hardware amplifier of ECGenius is the EPAMP, which acquires signals from third-party catheters and sensors connected to the patient. It then sends the signals to the ECGenius PC, which has a software program called the RECORDER SW that visualizes the signals to the user and provides the users a way to interactively analyze them. The following figure illustrates this signal pathway.

There are no parts of the tested medical device that may come into contact with the subject's body or body fluids. There are no medicinal products, human or animal tissues or their derivatives, or other biologically active substances used in the device.

Each manufacturing lot of investigational device part is assigned a unique lot number that is printed on the device package labeling, providing a means of traceability. A device accountability log will be used to track the use of devices in the study. The lot number will be recorded in each case report form.

3. RISK-BENEFIT ANALYSIS

There are no known risks to the potential subjects specifically associated with the use of the ECGenius®.

Potential risks include product failures similar to commercially available EP recording systems, with a similar likelihood of occurrence.

Risks associated with cardiac electrophysiology procedures include events reported in the literature related to catheter procedures, identified in the risk and hazard analyses, and associated with percutaneous interventions. A list of anticipated adverse events are defined in Section 6.5. Each adverse event and/or device effect will be evaluated in detail as described in Section 6 of this document.

The protocol is designed for parallel data collection during an electrophysiology study. The investigator diagnostic decisions will be guided by an approved EP recording system as per institution standard of care. Due to the protocol design and noninvasive nature of the tested medical device the rate of expected occurrence of SAEs or SADEs related to the use of the investigational device is low.

CathVision personnel will be responsible for the installation of the investigational device. During the study, the device will be operated by study trained site personnel.

As the treatment will be guided by an approved EP recording system the reduction in symptomatic arrhythmia will be similar to the benefit of currently available EP recording systems.

4. INVESTIGATIONAL PLAN

4.1 STUDY OBJECTIVES

The primary objective is to evaluate the safety and technical performance of the CathVision ECGenius® System. The secondary objective is to benchmark the intracardiac electrogram signal quality compared to commercially available systems in patients undergoing assessment and ablation of cardiac arrhythmias.

4.2 STUDY DESIGN

This is a prospective, multi-center, open-label, single arm study to evaluate the safety and technical performance of the CathVision ECGenius® system in up to 30 adult patients scheduled to undergo an EP procedure.

Intracardiac signals will be passively recorded in parallel with the commercial EP recording system. The tested device will not be used to direct clinical care decisions or therapy. The EP procedure will be guided by study site's standards of care. A summary of the schedules of evaluations and visits can be found in section 4.7.1.

4.3 STUDY DURATION

Study enrollment is planned for 1-3 months.

4.4 SUBJECT POPULATION

Up to 30 adult subjects will be enrolled in the study.

Eligible subjects must meet the inclusion and exclusion criteria described in Sections 4.4.1 and 4.4.2 to be enrolled in the study and undergo an EP procedure using the CathVision ECGenius® System.

4.4.1 INCLUSION CRITERIA

Subjects must meet all of the following inclusion criteria to be included in the study:

1. Patient scheduled for catheter ablation or diagnostic electrophysiology procedure.
2. At least 18 years of age.
3. Able and willing to provide informed consent from a legally authorized representative (LAR).

4.4.2 EXCLUSION CRITERIA

Subjects will not be eligible for the study if any of the following exclusion criteria are met:

1. Patient inability to understand or refusal to sign informed consent.
2. Current participation in another investigational drug or device study that interferes with this study
3. Patient is a prisoner or under incarceration
4. Patients who in the opinion of the physician are not candidates for this study.
5. Patients who are considered part of any vulnerable population.

4.5 STUDY OUTCOMES

4.5.1 PRIMARY OUTCOME

The Primary endpoint of the study will be evaluated as the technical success of CathVision ECGenius® System to collect and record intracardiac signals during routine EP procedures. Specifically:

- To record and plot low voltage electrograms
- To assess the improved signal (better signal to noise ratio) compared with the standard signal
- To visualize the shape and timing of electrograms

A defined evaluation scale for CathVision ECGenius signal versus the standard of care signal will be defined as 1 (best) to 5 (worse) for different areas of interest. This evaluation will be done by the institution principal investigator for both signal and mapping if available.

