4.7.4 VISIT 2: DAY 0 (INDEX PROCEDURE THROUGH DISCHARGE)

During the index EP procedure, institutional standard of care is to be utilized to treat the subject.

When the subject is connected to the standard EP recording system, during manipulation of catheters or diagnostic tests, intracardiac signals will be recorded using the investigational device in parallel. The total procedure time is not expected to differ by adding the CathVision ECGenius® system to the EP system as the final comparison of data recorded from the Standard EP recording system and the tested device will occur post procedure.

Prior to discharge, the following will be documented:

- Adverse events (AE)
- CathVision ECGenius device malfunctions
- Protocol deviations

Subjects will be considered to have completed and exit the study after this visit.

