## 5.6. Statistical analysis

Endpoint	Statistical method	Hypothesis & benchmark
Freedom from major adverse events, evaluated at hospital discharge.	
 
• Count number of AEs
 
• Percentage: [Procedures with AE] / [Total number of procedures]
 
	
 
• 3.5% of patients develop major AE within 30 days of procedure.
 
• Zero CathVision Cube-related AE are expected.
 

Recording low-voltage electrograms	
 
• Count number of low-voltage electrograms plotted in total
 
• Percentage: [Total number low-voltage electrogram plots] / [Total number of procedures]
 
• Physician user quantitatively score low-voltage electrogram plots on “ease” of interpretation of EGMs” [0-5] on CathVision Cube and on existing EP system 
 
○ 0: Impossible
 
○ 1: Very difficult
 
 
 
	
 
• At least one low-voltage electrogram plot per procedure
 
• CathVision not inferior to existing EP recording system
 

Document no.:	Effective Date:	Version: 1
Author: [name]	Approver:	Reviewer:

Endpoint	Statistical method	Hypothesis & benchmark
	
 
 2: Difficult
 
 3: Possible
 
 4: Easy
 
 5: Very easy
 
 
 
• Average physician score on CathVision ECGenius™ vs average physician score on existing EP system
 
	
Assessing the improved signal quality (baseline noise level peak-to-peak)	
 
• Peak-to-peak amplitude of baseline noise, on unipolar electrogram, at at least 1 site with low-voltage electrograms, and averaged if more than 1.
 
• Peak-to-peak amplitude of baseline noise, on bipolar electrogram, at at least 1 site with low-voltage electrograms, and averaged if more than 1.
 
• Non-inferior peak-to-peak amplitude of baseline noise to existing EP recording system.
 
	
 
• Hypothesis is below 50uV unipolar baseline noise peak-to-peak
 
• Hypothesis is below 20uV bipolar baseline noise peak-to-peak
 
• Hypothesis is non-inferior to existing EP recording system.
 

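### The opinion score that carries the non-inferiority benchmark for electrogram readability is given with no provision for masking, although masked scoring from recorded plots looks feasible

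*Protocol*

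**What the plan says.** Two opinion scores bear on the primary performance endpoint.

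- **SAP 5.6, row on recording low-voltage electrograms.** The entry reads "Physician user quantitatively score low-voltage electrogram plots on" ease of interpretation, from 0 (impossible) to 5 (very easy), on the CathVision system and on the existing system. The summary is "Average physician score on CathVision ECGenius™ vs average physician score on existing EP system", and the benchmark is "CathVision not inferior to existing EP recording system".
- **Protocol 4.5.1.** The ECGenius signal is rated against the standard-of-care signal from 1 (best) to 5 (worst) for different areas of interest. On the rater: "This evaluation will be done by the institution principal investigator for both signal and mapping if available".

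On the setting, Protocol 4.2 says: "This is a prospective, multi-center, open-label, single arm study to evaluate the safety and technical performance". The same section says that signals are recorded in parallel with the commercial system and that "The tested device will not be used to direct clinical care decisions or therapy". Protocol 4.7.4 says that "the final comparison of data recorded from the Standard EP recording system and the tested device will occur post procedure". The synopses allow up to two sites and up to 30 subjects.

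Neither document mentions masked plots, coding, random reading order or an independent reader.

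**The concern.** Ease of interpretation is a judgement on an ordinal scale, so it can take in what the rater expects as well as what the trace shows. Pressure is plausible in both directions. Protocol 8.6 provides sponsor-led training on the new device, and the endpoint itself is worded as assessing an improved signal. On the other side, Protocol 3 has diagnostic decisions guided by an approved system under the institution's standard of care, so the rater may find that display easier simply through familiarity.

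At stake is the meaning of the SAP's non-inferiority statement on this score. If the rater knows the source of each plot, a finding of no inferiority, or of inferiority, cannot be separated from rater preference. This is distinct from where noise is measured: it would remain even if both systems were scored at the same pre-specified site.

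**Working it through.** **1. The two instruments side by side**

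| | Protocol 4.5.1 | SAP 5.6 |
|---|---|---|
| Rater | Principal investigator | Physician user |
| Scale | 1 to 5 | 0 to 5 |
| Good end | Low | High |
| What is rated | ECGenius versus standard signal, several areas of interest; mapping if available | Ease of interpreting low-voltage plots, each system scored |
| Benchmark | None in this section | Non-inferior to existing system |
| Masking | None described | None described |

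A score of 5 is the worst grade on one scale and the best on the other. The non-inferiority benchmark belongs to the SAP score. The naming of the principal investigator belongs to the Protocol scale.

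**2. Does the rater know the source?** This is inferred from three things: the open-label design, the rater's role as investigator or user, and the absence of any masking provision. No sentence states it.

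**3. Could the rater be masked?** Recordings are parallel, the device does not direct care, and the final data comparison is made after the procedure. No clinical step is therefore seen to depend on the scorer knowing the source. The documents do not say when the physician score is given or whether the commercial system can export matched traces.

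**4. Does a preference average out?** Write each procedure's score difference (ECGenius minus existing, SAP scale) as true difference + preference of the rater + random error. Over n procedures, with rater r scoring n_r of them:

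mean difference = true difference + Σ (n_r / n) × b_r + mean error

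The random part shrinks as 1/√n. The preference term does not depend on n, only on how the raters' preferences combine. Assume, for illustration only, preferences of half a category:

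- One rater, b = +0.5: shift +0.5, which is 0.5 / 5 = 10% of the scale.
- Two raters with equal shares, both −0.5: shift −0.5.
- Two raters with equal shares, +0.5 and 0: shift 0.5 × 0.5 + 0.5 × 0 = +0.25.
- Two raters with equal shares, +0.5 and −0.5: shift 0.

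So a preference persists if it is shared, cancels if it is opposed, and can help or hurt ECGenius.

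**5. Can the documents size the effect?** No. The sample size reproduces as the mean of three other trials, (30 + 20 + 40) / 3 = 30 (SAP 5.5). Protocol 7.1 says no formal hypothesis was used to derive it. No margin, standard deviation, alpha or power is given for the score.

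**The case against.** The strongest reply has four parts.

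- **This is a declared open-label, largely descriptive study.** Protocol 7.1 and 7.2 support that. It stands only in part: the SAP attaches a non-inferiority benchmark to this score, and an unmasked preference shifts a descriptive mean difference just as it shifts a tested one.
- **Signal quality does not rest on opinion alone.** SAP 5.6 also has measured baseline noise, with limits of 50 µV unipolar and 20 µV bipolar and its own comparison with the existing system. This is correct and limits the seriousness. It does not protect the readability score, which has a separate benchmark.
- **Masking may change what is rated.** Protocol 2.1 makes the display software part of the system, and Protocol 1.3 names filter design as a source of artefact. Redrawing everything in one identical format could remove real differences. This stands, and it is why each system's own filtering should be kept and any rating of the full display reported separately.
- **The sentence on post-procedure comparison explains why procedure time should not lengthen.** It does not schedule the physician score, which could be a bedside rating. This also stands; it supports feasibility only.

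A reader might infer that exactly two raters, both of whom guided the cases, tilt every procedure towards ECGenius. The documents do not support this. The physician user is not limited to one person per site, no section says that the principal investigator performs each case, and neither the existence nor the direction of a preference is known.

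**Conclusion.** The point holds as an avoidable risk of rater bias in one component of the primary performance endpoint. An opinion score with a non-inferiority benchmark is given in an open-label study with no masking provision, and masked scoring looks feasible. It should be changed, but it does not undermine the noise measurements or the safety endpoint.

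The conclusion rests on two inferences: that the rater knows the source of each plot, and that raters are few (at most two only if the principal investigators alone score). The bias could run in either direction.

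A reader might go further and quote an inflated error rate. Take a one-sided 0.025 paired t test with n = 30, a true difference exactly at the margin, and a standard deviation of paired differences between 0.75 and 1.5. A uniform 0.25-point preference for ECGenius would raise false non-inferiority from 2.5% to between 14% and 42%, and a 0.5-point preference to between 42% and 94%. Every one of these inputs is assumed. The SAP specifies no such test, alpha or standard deviation; 30 is a ceiling on enrolment towards which screen failures after the screening visit count (Protocol 4.7.3); and a preference for the existing system would work against a non-inferiority finding. These figures show sensitivity only and are not the size of the problem.

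**What to change.** Amend Protocol 4.5.1 and SAP 5.6 together:

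1. Use one scale, one direction and one named rater for the ease-of-interpretation comparison.
2. Have that same physician score after the procedure from paired plots of the same beats and channels. Remove system labels and identifiers, and match gain and sweep speed where export allows. Keep each system's own signal filtering.
3. Code the plots, present them in random order, and lock the scores before the code is opened.
4. Base the non-inferiority statement on the masked scores. Report any unmasked bedside or mapping rating separately, as descriptive.

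The cost is wording in two documents and some file preparation and coding. No extra reader, visit or subject is needed. Masking will be imperfect if a trace is recognisable or the case is recalled, and export from the commercial system must be confirmed. The masked score rates the signal rather than the whole display; the separate unmasked rating covers the latter.
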